3.4.1.2 Sensitivity Analyses

- Sensitivity analysis 1: Multiple Imputation (MI) under Missing at Random

If there is missing data in the 3CS score, a multiple imputation model for missing observations will be constructed from the observed data under the MAR assumption. The imputation model will include nasal polyp stratum, baseline score, treatment group and post-baseline scores to impute the missing 3CS score with monotone regression method and MCMC method will be used to produce monotone missing pattern (by treatment). There will be 100 imputed datasets derived using SAS PROC MI based on the pre-specified model above with a given random seed (protocol date). The same MMRM model will be performed on each dataset after imputing the missing scores and PROC MIANALYZE will be used to combine the results.

- Sensitivity analysis 2: Tipping Point Analysis for Missing Not at Random (MNAR)

If there is missing data in the 3CS score, tipping point analysis will be used to impute missing value at 24 weeks as follows.

- Step 1. Monotone missing pattern was induced by Markov Chain Monte Carlo (MCMC) method using PROC MI: for patients who have intermediate missing values, the intermediate missing values will be imputed assuming a multivariate normal distribution over observations from all visits. 100 datasets with a monotone missing pattern will be obtained using this method with a given random seed (protocol date).
- Step 2. For each of the imputed dataset with monotone missing pattern obtained in Step 1, the remaining missing data will be imputed using the regression method for the monotone pattern with adjustment for covariates including response variable, treatment groups, nasal polyp status, and baseline value. All available data in the monotone missing pattern data will be used. One imputed dataset will be obtained for each of the imputed dataset at Step 1. So, 100 fully imputed datasets will be obtained altogether.
- Step 3. The imputed values in LYR-210 group are added by a positive amount d (by 0.5 from 0 to 9) for each imputed data sets.
- Step 4. The imputed values in sham group are subtracted by a positive amount p (by 0.5 from -9 to 0) for each imputed data sets.
- Step 5. Change from baseline in endpoint will be analyzed using ANCOVA model same as the one in primary analysis. Then the SAS MIANALYZE procedure will be used to generate statistical inferences by combining results from the 100 analyses using Rubin's formula.

Step 3 to Step 5 will be repeated iteratively until the p-value for treatment effect of LYR-210 compared to sham estimated in Step 5 is >0.05 .

LS mean difference between LYR-210 and sham in change from baseline of 3CS score at Week 24 and the corresponding p-values will be provided for each combination of shift parameters.

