2.2.4 Sample Size Determination

Per the null and alternative hypotheses described in Section 3.1.6, 2:1 randomization (LYR-210:control), in the participants without polyps, [REDACTED]

With a sample size of 150 participants (n=50 control and n=100 LYR-210), alpha = 0.05, and power of 0.95, we will be able to detect an effect size of 0.63, which represents a mean difference of 1.31. This effect size is 18% smaller than the observed difference in the Phase 2 study (1.61 versus 1.31 3CS mean change scores). For the first key secondary endpoint (an analysis of the primary endpoint in all participants; n=60 control and n=120 LYR-210), the study will have 95% power to detect an effect size of 0.57, which represents a mean difference of 1.19.

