3.1.6 Hypothesis Testing

For the primary efficacy endpoint, the null and alternative hypotheses to be tested are:

$$H_0: \mu_L = \mu_C$$

vs

$$H_1: \mu_L \neq \mu_C$$

where μ_L and μ_C are true mean CFBL in 3CS at Week 24 for participants receiving the LYR-210 (7500 μ g) treatment and the control (sham) treatment, respectively.

Unless otherwise specified, all hypothesis tests will be conducted at a 2-sided significance level of 0.05. Two-sided equal tailed 95% (asymptotic) confidence intervals (CIs) will also be calculated.

[figure not shown]

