3.4.1.1 Primary Analysis Method

The primary analysis to test difference between LYR-210 and sham in the mean change from baseline in 3CS score at week 24 will be performed on the ITT Analysis Set without nasal polyp using a mixed model with repeated measures (MMRM).

The MMRM will use change from baseline as the dependent variable, and include the fixed, categorical effects of treatment, visit, treatment-by-visit interaction, and covariates of baseline score and baseline score-by-visit interaction. An unstructured covariance structure shared across treatment groups will be used to model the within-subject errors. The covariance parameters in the above model will be fitted through a working model that assumes joint multivariate normality (MVN) of responses by maximizing the restricted likelihood (REML) under the working model, and the mean parameters will be estimated by generalized least squares after plugging in REML estimate of covariance parameters. In case the model does not converge with the unstructured covariance structure, the heterogenous Toeplitz structure (TOEPH) will be used instead. In case the model will not converge with the TOEPH structure, heterogenous compound symmetry (CSH) will be used instead. The Kenward-Roger approximation will be used to estimate denominator degrees of freedom and adjust nominal standard errors based on the inverse observed information from the working MVN model. Missing data will be handled by the MMRM under the missing at random (MAR) assumption. The impact of this assumption will be evaluated by sensitivity analyses specified in Section 3.4.1.2.

Least-squares means (LS-means) for change from baseline at each analysis visit will be provided for each treatment group and the difference in LS means between LYR-210 and sham treatment at each analysis visit, corresponding standard error, two-sided 95% confidence intervals and two-tailed p-value will be estimated from the MMRM model.

Descriptive summary statistics on the values and changes from baseline will be presented for the 3CS score at each analysis visit by treatment group.

Graphic displays of the results will be presented. The by-visit means and the standard errors for each treatment will be plotted by the analysis visit. In addition, the by-visit least squares mean changes and the standard errors for each treatment will also be plotted by the analysis visit.

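### SAP 3.4.1.2 Step 4 contradicts itself on the direction of the sham shift; taken by its printed range, the sham side of the only missing-not-at-random analysis would favour LYR-210

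*SAP*

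**What the plan says.** SAP 3.4.1.1 fits an MMRM to the Week 24 change in 3CS and assumes missing at random. Of that assumption it says: "The impact of this assumption will be evaluated by sensitivity analyses specified in Section 3.4.1.2".

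SAP 3.4.1.2 has two analyses. The first is multiple imputation, again under missing at random. The second is a tipping-point analysis for missing not at random:

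- Step 3, active arm: "The imputed values in LYR-210 group are added by a positive amount d (by 0.5 from 0 to 9").
- Step 4, control arm: "The imputed values in sham group are subtracted by a positive amount p (by 0.5 from -9 to 0").
- Step 5, model: "Change from baseline in endpoint will be analyzed using ANCOVA model same as the one in primary analysis".

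Steps 3 to 5 are then repeated until the p-value passes 0.05. The text does not say how d and p move relative to each other, but it does ask for the Week 24 difference and p-value at every combination of the two shifts.

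The direction of the score is clear. SAP 3.1.4.1 and 3.1.4.2 grade each of three symptoms from 0 (none) to 3 (severe) and add them, so 3CS runs from 0 to 9 and higher is worse.

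**The concern.** A tipping-point analysis has to move imputed values against the experimental arm. Step 3 does so, because adding d worsens LYR-210. The counterpart is to improve sham by lowering its imputed scores.

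Step 4 gives two incompatible instructions. Subtracting a positive amount lowers the scores. But no value in the printed range is positive, and subtracting a value between -9 and 0 raises them. In Step 3 the bracket lists the values of the amount applied. A programmer who reads Step 4 the same way would worsen sham, and that offsets the LYR-210 penalty or adds to the apparent benefit.

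Nothing else in the plan covers this. Sensitivity analysis 1 keeps missing at random, and the supplementary analyses in SAP 3.4.1.3 change the analysis set or the handling of systemic corticosteroids and surgery. A fragile primary result could therefore look sturdier than it is.

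**Working it through.** **Inputs from the documents**
- Two-sided testing: "all hypothesis tests will be conducted at a 2-sided significance level of 0.05" (SAP 3.1.6).
- Size: "With a sample size of 150 participants (n=50 control and n=100 LYR-210), alpha = 0.05, and power of 0.95" (SAP 2.2.4).
- Effect: "detect an effect size of 0.63, which represents a mean difference of 1.31" (SAP 2.2.4). Implied SD = 1.31 / 0.63 = 2.08.
- Grid: 0 to 9 by 0.5 gives 19 values per arm, so 19 x 19 = 361 cells.

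**Assumptions.** The missing fraction m is not in the documents. It is taken as equal in both arms, from 5% to 30%. The missing-at-random difference is set at the design value, -1.31.

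**The plan's own figures.** Power = Φ(0.63 / √(1/50 + 1/100) - 1.96) = Φ(1.68) = 0.953, as stated. For all participants, "95% power to detect an effect size of 0.57, which represents a mean difference of 1.19" with 60 and 120: Φ(0.57 / √(1/60 + 1/120) - 1.96) = 0.950. Both reproduce, so the SD is a sound input.

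**Formula for each cell.** Let s be the signed change applied to imputed sham values: s = +p in size under the printed range, s = -p when corrected.

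Estimate = -1.31 + m·d - m·s

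Variance = (1/100 + 1/50) × [SD² + m(1 - m)(100d² + 50s²)/150 + SD²·m/(1 - m)]

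The middle term is the extra spread from shifting a fraction of each arm. The last approximates the between-imputation variance. A normal reference is used.

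**One cell by hand: m = 10%, both shifts 4.** Bracket = 4.324 + 0.09 × 16 + 4.324 × 0.1111 = 6.244. SE = √(0.03 × 6.244) = 0.433.
- Printed range: -1.31 + 0.4 - 0.4 = -1.31; z = -3.03; p about 0.002.
- Corrected: -1.31 + 0.4 + 0.4 = -0.51; z = -1.18; p about 0.24.

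**The p = 0 line: m = 10%, d = 5.** Estimate = -1.31 + 0.5 = -0.81. Bracket = 4.324 + 0.09 × 2500/150 + 0.480 = 6.304; SE = 0.435; p about 0.06. This line tips whichever way Step 4 is read.

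**Smallest shift at which significance is lost**

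| Missing per arm | LYR-210 alone (either reading) | Sham alone, printed range | Sham alone, corrected | Both together, printed range | Both together, corrected |
|---|---|---|---|---|---|
| 5% | 8.5 | never | never | never | 5.0 |
| 10% | 5.0 | never | 5.5 | never | 3.0 |
| 15% | 3.5 | never | 3.5 | 9.0 | 2.0 |
| 20% | 2.5 | never | 2.5 | 8.0 | 1.5 |
| 30% | 1.5 | never | 2.0 | 6.5 | 1.0 |

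Under the printed range, moving both together leaves the estimate at -1.31. The late losses at 15% and above come only from variance inflation. Moving sham alone by 9 enlarges the benefit: -1.31 - 0.05 × 9 = -1.76, -1.31 - 0.10 × 9 = -2.21 and -1.31 - 0.20 × 9 = -3.11 at 5%, 10% and 20% missing. If 20% of sham and 10% of LYR-210 are missing, a shift of 4 in both gives -1.31 + 0.4 - 0.8 = -1.71.

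**Non-significant cells out of 361, printed range against corrected:** 3 against 156 at 5% missing; 70 against 298 at 10%; 139 against 271 at 20%. At 20%, another 73 corrected cells are significant in favour of sham, so LYR-210's benefit is lost in 271 + 73 = 344.

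**Smaller observed difference, 10% missing:** 151 against 346 cells at -1.0; 208 against 358 at -0.8.

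**Step 5 model.** On one simulated complete dataset, a Week 24 ANCOVA and an unstructured MMRM gave the same contrast, -1.559 (SE 0.588).

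**The case against.** The best defence is that this is a slip of notation. The verb phrase gives the right direction, and the bracket can be read as the signed shift to be added, mirroring 0 to 9 in Step 3. The purpose of the analysis and the rule of repeating until significance is lost both fit that reading. SAP section 6 leaves detailed programming to a separate document, which may have the sign right. All of this is fair. It means that the SAP cannot be said to prescribe the wrong direction outright. It does not remove the contradiction, because one of the two phrases must be disregarded to program the step.

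A reader might go further and infer that the analysis cannot tip at all. The documents do not support that. Step 3 is correct, and results are required at every combination of shifts, including p = 0, where the sign of p is irrelevant and the table shows tipping at every missing fraction examined.

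A reader might also infer that Step 5 cites a model that does not exist. That is too strong. Protocol 9.3.2 itself describes the MMRM as a form of analysis of covariance, and on completed data the two models give the same Week 24 contrast. The label is imprecise but changes no result.

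Finally, the primary estimate and its p-value do not depend on this step. That stands.

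**Conclusion.** The point holds as an internal contradiction in the sham shift of the plan's only missing-not-at-random analysis. If the printed range is followed, the sham-side stress is reversed and the joint stress largely cancels; the LYR-210-only stress survives. At the design difference, the share of the grid showing loss of significance falls from 298/361 = 83% to 70/361 = 19% at 10% missing, and from 156/361 = 43% to 3/361 = 1% at 5%.

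The contradiction can be read directly from the text. The sizes rest on assumed and equal missing fractions, an assumed missing-at-random difference, the SD implied by the sample-size statement, and an approximate rather than a full multiple-imputation variance. The risk is greatest if d and p are stepped together: on the printed range at 5% to 10% missing, such a search ends without a tipping point. The correction should be made before database lock.

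**What to change.** Rewrite Step 4 to say that each imputed sham value is lowered by p, with p running from 0 to 9 in steps of 0.5. Equivalently, a signed shift from -9 to 0 is added. One line stating that this improves sham would settle the direction.

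Keep the existing requirement to report every d-by-p combination, and say that the full grid, not a paired search that stops at the first p-value above 0.05, is the deliverable.

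As a clarification only, name the Step 5 model: a Week 24 ANCOVA with treatment and baseline score, or the primary MMRM fitted to the completed data.

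The cost is a few sentences of SAP text, and a check that the programming specification agrees. SAP section 1 places approval of the final version before the Week 24 database lock, so it fits the existing timetable. No data, visits or participants are affected.

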3.4.1.3 Supplementary Analysis

- The same MMRM model defined in the primary analysis will be performed based on the Per-Protocol Population

Additional sensitivity analyses (supplementary estimands) will be conducted by the following alterations of the primary estimand regarding the handling of intercurrent event of SCS use or ESS while keeping the same strategy as the primary estimand for the other intercurrent events.

- 1) Supplementary 1: Treatment policy strategy for the use of SCS for any indication or ESS
- 2) Supplementary 2: Composite strategy of participant's worst post-baseline value for SCS for CRS indication and ESS; Treatment policy for SCS use for other indication.

3.4.2 Key Secondary Efficacy Endpoints

The estimand attributes for the following key secondary efficacy endpoints are defined in the same manner as for primary efficacy endpoint in Section 3.4.1:

1. CFBL in the 7-day average composite score of 3CS at Week 24 in all participants.

2. CFBL in the 22-item Sino-Nasal Outcome Test (SNOT-22) total score at Week 24 in all participants.

The same analysis methods used for the primary efficacy endpoint will be used for the above key secondary efficacy endpoints by including an additional term for polyp status as a stratum. The LS-means for change from baseline at each analysis visit will be provided for each treatment group and the difference between LYR-210 and sham treatment at each analysis visit will be estimated along with the CIs. The p-value for the comparison at each analysis visit will also be presented.

3. CFBL in the percent opacification of the bilateral anterior and posterior ethmoids at Week 20 as determined by 3-D volumetric CT analysis in all participants.

The above endpoints will be analyzed by ANCOVA with fixed-effect terms for treatment group and nasal polyp status. LS-means in each treatment group and their difference with 95% confidence interval (CI) and p-value will be provided.

4. Rescue treatment requirement through Week 24

Rescue treatment requirement through Week 24 will be summarized descriptively. Statistical comparisons between Lyra and Sham groups will be conducted on the pooled data with ENLIGHTEN 2 according to the integrated summary of efficacy SAP following the prespecified hierarchical testing method to adjust the multiplicity adjustment.

Descriptive summary statistics on the values and changes from baseline will be presented for the above key secondary efficacy endpoints at each analysis visit by treatment group.

In addition, the point estimate and the two-sided 95% exact binomial confidence intervals (using the Clopper-Pearson method) will be presented for the proportion of subjects requiring rescue treatment through Week 24 will be tabulated by treatment group in the ISE.

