9.3.2 Analysis methods

Data collected in this study will be presented using listings, summary tables, and figures. Continuous data will be summarized by treatment group using the following descriptive statistics: the number of observations (n), mean, SD, median, minimum, and maximum. Categorical data will be summarized by treatment group as number and percentage of participants in each category. Individual participant's data will be presented in listings.

For cardinal symptoms (3CS and individual symptoms), the baseline score is the average of nonmissing daily scores over the 7-day period prior to and including Day 1. For other efficacy and safety assessments, the baseline value is the last nonmissing value prior to treatment administration.

Unless otherwise specified, all hypothesis tests will be conducted at a 2-sided significance level of 0.05 and all confidence intervals will be constructed 2-sided with a confidence level of 95%.

The primary analysis method for the primary endpoint will be a mixed models repeated measures analysis of covariance (MMRM) with treatment group, week and nasal polyp status (grade 1 polyp vs no polyp) as factors, with baseline measurement as covariate, an interaction of

treatment by week and an interaction of baseline measurement by week. The primary analysis will be conducted according to the primary estimand that is specified in Table 1. Sensitivity analysis will be conducted to assess the impact of the missing at random assumption in the MMRM. Additionally, supplemental analyses will be conducted to assess the robustness of the primary analysis according to the prespecified plan in the SAP. The LS mean change for each treatment group, the LS mean difference between treatment groups, as well as the corresponding 95% confidence intervals and p-values will be reported.

Changes from baseline to continuous endpoints will be analyzed using an MMRM or ANCOVA as appropriate which will be prespecified in the SAP.

Time-to-event endpoints will be analyzed using the Kaplan-Meier (K-M) method. The K-M curves will be compared between treatment groups using the log-rank test.

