Responder endpoints (eg, improvement of ≥ 8.9 in SNOT-22 and improvement of ≥ 1 point, ≥ 2 points, ≥ 3 points in 3CS) will be analyzed using the CMH test controlling for geographic region and nasal polyp status. Participants who receive SCS for any reason and/or are indicated for sinonasal surgery will be considered nonresponders for time points after SCS use or surgery. Unless otherwise specified, participants with missing data will be included as nonresponders.

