9.3.7 Efficacy analyses

Hypothesis testing for all efficacy endpoints will be conducted on the ITT population. The study level type-1 error for the family of primary and key secondary efficacy hypotheses will be controlled at alpha of 0.05. Unless otherwise noted, all analyses of efficacy outcome measures will be adjusted for baseline score, geographic region, and nasal polyp status. Adjustment by additional covariates, if any, will be described in the SAP.

All efficacy analyses will be carried out after the last participant completes the blinded Week 24 visit or withdraws prematurely before Week 24, and all data from the 24-week study period have been entered into the study database, cleaned, verified, and locked.

Efficacy data collected during the safety extension phase will be summarized descriptively.

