3.4.3 Additional Secondary Efficacy Endpoints

The endpoints derivation and data handling are described in Section 3.1.4. The numbering of the following endpoints is consistent with Section 2.3.3.

- o CFBL in the 22-item Sino-Nasal Outcome Test (SNOT-22) total score at Week 24 in participants without nasal polyps
- o CFBL in 3CS score at Weeks 4, 8, 12, 16, and 20
- o CFBL in the symptom score for individual cardinal symptoms of nasal blockage/obstruction/congestion, anterior/posterior nasal discharge, and facial pain/pressure at Weeks 4, 8, 12, 16, 20, and 24
- o CFBL in loss of smell score at Weeks 4, 8, 12, 16, 20, and 24, for all participants and for participants with baseline score ≥ 2
- o CFBL in SNOT-22 total score at Weeks 4, 8, 12, 16, and 20
- o CFBL in SNOT-22 subdomain scores at Weeks 4, 8, 12, 16, 20, and 24

The endpoints above will be analyzed similarly to the primary efficacy endpoint but without the sensitivity analysis and supplemental analysis, and the data derivation and handling are described in Section 3.1.4. LS-means of the CFBL in each treatment group and their difference with 95% confidence interval (CI) and p-value will be provided.

- Improvement of ≥ 1 point, ≥ 2 points, and ≥ 3 points from baseline in 3CS score at Week 24
- Improvement of ≥ 8.9 and ≥ 12 from baseline in SNOT-22 total score at Week 24
- Sinonasal surgery requirement through Week 24
- Rescue medicine use through Week 24

- Improvement of ≥ 1 category and ≥ 2 categories in the severity of CRS-related symptoms as indicated by the Patient Global Impression of Severity (PGIS) at Week 24
- Overall change of "very much better" or "much better" in the CRS-related symptom severity as indicated by the Patient Global Impression of Change (PGIC) at Week 24

Participants who receive SCS for any reason and/or are indicated for sinonasal surgery will be considered non-responders for time points after SCS use or surgery. Unless otherwise specified in Section 3.1.4, participants with missing data will be included as non-responders. Comparison between LYR-210 group and the sham procedure group will be performed using logistic regression including nasal polyp status and baseline value. The general association p-value will be provided. The odds ratio and the corresponding CI will also be provided.

- CFBL in the percent opacification of the bilateral anterior and posterior ethmoids at Week 20 as determined by 3-D volumetric CT analysis in participants without nasal polyps

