- CFBL in the Zinreich score of the bilateral anterior and posterior ethmoids at Week 20
- CFBL in 36-Item short form health survey, version 2 (SF-36v2) physical health, mental health, and domain scores at Week 24
- CFBL in Medical Outcomes Study Sleep Scale (MOS Sleep-R) score at Week 24

The above endpoints will be analyzed by ANCOVA with fixed-effect terms for treatment group and nasal polyp status, and with baseline score as a covariate. LS-means in each treatment group and their difference with 95% confidence interval (CI) and p-value will be provided.

- Time to first rescue treatment requirement through Week 24

Time to first rescue treatment requirement through Week 24 will be analyzed using the Kaplan-Meier (K-M) method. The K-M estimate of median time to first recommendation of rescue treatment requirement with CI (if estimable) will be presented for each treatment group. Estimates of quartiles (25th and 75th percentiles) will also be presented for each treatment group. Time to first recommendation of rescue treatment will be compared between LYR-210 group and the sham procedure group using the log-rank test stratified by the stratification factor. P-value from the log-rank test will be presented.

- Total SCS dose prescribed through Week 24
- Number of days on SCS through Week 24

The above endpoints will be analyzed by ANCOVA with fixed-effect terms for treatment group and nasal polyp status. LS-means in each treatment group and their difference with 95% confidence interval (CI) and p-value will be provided.

Counts and percentages of subjects taking SCS medications by ATC class and preferred term will be summarized.

- CFBL in EuroQoL 5-dimension, 5-level (EQ-5D-5L) score at Week 24

The EQ-5D-5L descriptive system will be summarized as categorical variables by presenting the frequency and proportion of each level for each dimension by visit and by treatment arm, and analyzed by the Cochran–Mantel–Haenszel (CMH) test controlling for nasal polyp status and baseline score.

The overall health score on a 100-point vertical (visual analogue scale: 0 = worst imaginable health state; 100 = best imaginable health state) will be summarized as continuous variable and analyzed by ANCOVA including fixed-effect terms for treatment group and nasal polyp, and with baseline score as a covariate. LS-means in each treatment group and their difference with 95% confidence interval (CI) and p-value will be provided.

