- CFBL in Work Productivity and Activity Impairment-Specific Health Problem (WPAI-SHP), version 2.0 at Weeks 4, 12, and 24

The following will be summarized by visit and analyzed by ANCOVA including fixed-effect terms for treatment group and nasal polyp status, and baseline value as covariate. LS-means in each treatment group and their difference with 95% confidence interval (CI) and p-value will be provided.

- Percent work time missed due to CRS: $Q2/(Q2+Q3) \times 100\%$
- CRS affected productivity: $Q5 \times 10\%$
- CRS affected ability to do regular daily activities, other than work at a job: $Q6 \times 10\%$

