5 CHANGES FROM PROTOCOL

There is no change from the protocol-specified statistical analyses.

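### The confirmatory CT opacification endpoint is given an ANCOVA with no baseline covariate, unlike every other visible change-from-baseline model in the SAP; region handling also needs reconciling

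*SAP*

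**What the plan says.** **The CT model.** SAP 3.4.2 places change in percent opacification of the ethmoids at Week 20, in all participants, third among the key secondary endpoints. It is tested at two-sided 0.05 in the fixed sequence. The model sentence is: "The above endpoints will be analyzed by ANCOVA with fixed-effect terms for treatment group and nasal polyp status".

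**The default.** Protocol 9.3.7 states: "Unless otherwise noted, all analyses of efficacy outcome measures will be adjusted for baseline score, geographic region, and nasal polyp status".

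**The neighbouring models.** SAP 3.4.3 analyses the same CT measure in participants without polyps, together with Zinreich, SF-36v2 and MOS Sleep-R, using "fixed-effect terms for treatment group and nasal polyp status, and with baseline score as a covariate". WPAI-SHP is "analyzed by ANCOVA including fixed-effect terms for treatment group and nasal polyp status, and baseline value as covariate". The EQ-VAS ANCOVA, the CMH test for the EQ-5D-5L dimensions and the MMRM for the primary and first two key secondary endpoints also include baseline.

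**Region.** Randomization is stratified by region and polyp status (SAP 2.2.2). The primary MMRM in Protocol 9.3.2 uses "treatment group, week and nasal polyp status (grade 1 polyp vs no polyp) as factors, with baseline measurement as covariate", with no region term. For responder endpoints, Protocol 9.3.2 says they "will be analyzed using the CMH test controlling for geographic region and nasal polyp status", whereas SAP 3.4.3 says: "Comparison between LYR-210 group and the sham procedure group will be performed using logistic regression including nasal polyp status and baseline value". SAP Section 5 states: "There is no change from the protocol-specified statistical analyses".

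**The concern.** As written, the CT model is an ANCOVA without a covariate: an unadjusted comparison of change scores with a polyp factor. It is the only visible change-from-baseline model in the SAP that lacks baseline, and it belongs to a confirmatory endpoint.

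Baseline is likely to matter here. The score runs from 0% to 100%, entry requires only 5% opacification on each side, and possible improvement is capped by the starting value. Randomization does not stratify on CT severity, so the design does not protect against imbalance on it.

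The protocol default and the SAP model give two different analyses, hence two possible p-values, for one confirmatory test. CT is the last endpoint tested within this study, so a miss loses the CT claim. Any effect on the pooled rescue-treatment test depends on the integrated summary of efficacy (ISE) SAP.

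**Working it through.** **1. The plan's own figure.** No power, SD or effect size is given for CT. The nearest figure, for the first key secondary in all participants (60 sham, 120 LYR-210), reproduces. The detectable effect at 95% power is (1.960 + 1.645) × √(1/60 + 1/120) = 3.605 × 0.158 = 0.570, matching the stated 0.57. Power at 0.57 is 0.950 (normal) or 0.948 (t). The sample-size statement is not in dispute.

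**2. Does the CT wording imply baseline?** SAP 3.4.3 uses the same sentence, without baseline, for total systemic corticosteroid (SCS) dose and days on SCS. Those are not change-from-baseline endpoints and have no baseline score. In this SAP that sentence therefore describes a model without baseline, and a programmer following 3.4.2 would omit it.

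**3. Cost in precision.** Let rho be the baseline to Week 20 correlation and k the follow-up SD divided by the baseline SD, both taken as the same in each arm. Neither is in the documents, so ranges are assumed.

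- Variance with baseline relative to without: k²(1 − rho²) / (1 + k² − 2·rho·k).
- With k = 1 this is (1 + rho)/2.
- Denominator minus numerator is (1 − rho·k)², which is never negative, so the ratio never exceeds 1.
- CI widening from omission: 1/√ratio − 1.
- Equivalent N: 180 × ratio.
- Power of the unadjusted test if the adjusted test has 90%: Φ(3.242·√ratio − 1.960).

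**4. Baseline imbalance.** The SE of the baseline mean difference is √(1/120 + 1/60) = 0.158 SD. About 1 trial in 20 therefore has an imbalance above 1.96 × 0.158 = 0.31 SD in one direction or the other. With k = 1, an imbalance of that size shifts the unadjusted comparison by (1 − rho) × 0.31 SD.

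Results for k = 1:

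| rho | Variance ratio | CI widening | Equivalent N | Unadjusted power (adjusted 90%) | Shift at 0.31 SD imbalance |
|---|---|---|---|---|---|
| 0.3 | 0.65 | 24% | 117 | 74.3% | 0.22 SD |
| 0.5 | 0.75 | 15% | 135 | 80.2% | 0.15 SD |
| 0.7 | 0.85 | 8% | 153 | 84.8% | 0.09 SD |
| 0.9 | 0.95 | 3% | 171 | 88.5% | 0.03 SD |

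With k from 0.7 to 1.3 and rho from 0.3 to 0.7, the ratio runs from 0.417 (k = 0.7, rho = 0.3) to 0.991 (k = 1.3, rho = 0.7), so the CI widens by 55% down to 0.5%.

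**5. Validity.** A simulation with 120 vs 60 participants, the polyp factor in both models, k = 1 and 6,000 trials per rho gave type I error of 0.043 to 0.053 with or without baseline. The SE ratios (without to with baseline) were 1.24, 1.15, 1.08 and 1.02, in line with the table.

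**6. Region, by comparison of text.** Protocol 9.3.7 includes region by default; the primary MMRM in Protocol 9.3.2 does not list it; no SAP MMRM, ANCOVA or logistic model names it. For responders the protocol names both the test and region, and the SAP changes the test and drops region. The stratified log-rank test in SAP 3.4.3 refers to a single stratification factor, although there are two.

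**The case against.** The strongest reply on CT is that the documents, read together, already require baseline. The protocol default applies unless an exception is noted, silence is not an exception, the SAP declares no change, and the word ANCOVA implies a covariate. The sentence also refers to endpoints in the plural where only one is meant, which suggests carried-over text. A drafting slip is quite possible. But the identical wording for the SCS endpoints defeats the reading that ANCOVA here implies baseline, and the remedy is the same whether this is a slip or a choice.

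On size, the range is assumption-driven and runs from trivial to large. The imbalance figures are not a second harm on top of the wider interval: averaged over trials, they are the same variance. Any loss works against the sponsor and does not favour a false claim. All of that stands.

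On region, the default in Protocol 9.3.7 yields where something else is noted, and the specific MMRM listing in 9.3.2 can be read as such a note. That section also leaves the choice of MMRM or ANCOVA for continuous endpoints to the SAP. Region is therefore a matter to reconcile and not a proven error. In the linear models its omission is at most conservative, and the gain from adding it may be near zero. The responder text further promises a general association p-value, a term from CMH testing, so the intended test is unclear. The responder and time-to-rescue endpoints lie outside the hierarchy, so no alpha-controlled claim rests on them.

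**Conclusion.** The concern holds. As written, the CT key secondary model omits baseline, against the protocol default and the SAP's own practice for the same measure. The test is valid, and the cost is efficiency. With equal SDs at the two scans, the CI is about 24% to 3% wider for correlations of 0.3 to 0.9. Over the wider grid of SD ratios and correlations the widening is 55% to 0.5%. No combination favours leaving baseline out, apart from the one degree of freedom it uses. These sizes rest on assumed correlations and SD ratios, common to both arms, because the documents give none for CT.

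The region point is separate and lesser. Its firm part is the undeclared responder change: CMH controlling for region and polyp status in the protocol, logistic regression without region in the SAP, and a statement that nothing changed. This should be corrected before unblinding, but it does not threaten the validity of the trial.

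**What to change.** 1. In SAP 3.4.2, add baseline percent opacification as a covariate in the CT ANCOVA. This costs one degree of freedom and uses the screening CT value. No data are lost, because a change score cannot be computed without that value.
2. State one rule for region across Protocol 9.3.2, Protocol 9.3.7 and the SAP. Either add region as a main effect to the MMRM, ANCOVA and responder logistic models, or declare its removal in SAP Section 5. This is a text edit, plus one term per model if region is added.
3. In either case, declare the change from CMH to logistic regression in SAP Section 5, and say which test supplies the responder p-value.
4. Name the log-rank strata. With about 30 polyp participants at 2:1, about 10 are sham participants spread over two regions, so region-by-polyp cells may be sparse. Prespecify a single factor or a pooling rule.
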